- Immediate hypersensitivity reactions including urticaria, anaphylaxis, or other IgE-mediated responses are possible as with any vaccine.
- MAAEs will be collected during the Acute Phase for either vaccination using the same process as other AEs.
- SAEs will be recorded throughout the participant's participation in the study. The participant's parent / guardian / legally authorized representative will be asked to notify the site immediately about any potential SAE at any time during the study. In addition, the participant's parent / guardian / legally authorized representative will record information in a DC / eDC about SAEs from the D0 to D56 visits (Cohorts 1 and 3), and from D0 to D84 visits (Cohorts 2 and 4). Participant's parent / guardian / legally authorized representative receives a memory aid (MA) to record the SAEs from the D56 visit until the end of the study (Cohorts 1 and 3) and from the D84 visit until the end of the study (Cohorts 2 and 4).
- The completed DC / eDC or MA will be reviewed with the participant's parent / guardian/ legally authorized representative at each visit.

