- 11) Give or download the parent / guardian / legally authorized representative a diary card (DC3) / eDC and a thermometer and go over the instructions for their use, as detailed in the Study Operating Guideline, and remind to complete the Day 0–7 pages of DC3 / eDC. The parent / guardian / legally authorized representative will record the child's temperature and signs of illness (solicited reactions and unsolicited AEs, including AESIs, MAAEs and SAEs) on the DC3 / eDC.
- 12) Remind the parent / guardian / legally authorized representative to expect a telephone call from the study site nurse daily after this Visit 04 to review what they have entered daily in the DC3 / eDC, and to complete the entries of DC3 and bring to Visit 05 at the specified date and time.
- 13) Remind the parent / guardian / legally authorized representative to notify the site in case of an SAE or any illness. The site staff, upon evaluation, will schedule an Illness Visit within the stipulated time frame of site notification, if required.
- 14) Complete the relevant CRFs for this visit.

Post-RSV Season or ≥ 5 Months After Last Vaccine Administration Visit for All Cohorts (Visit 04 for Cohorts 1 and 3 or Visit 06 for Cohorts 2 and 4)

- 1) Obtain a blood sample for serum antibodies to RSV.
- 2) Review the MA for SAEs with the participant's parent / guardian / legally authorized representative.
- 3) If an SAE had occurred, follow the instructions in [Section 10](#) for reporting it. Remind to notify the site in case of an SAE.
- 4) Complete the relevant CRFs for this visit and the End of Study CRF.

Visit 04: D63+7 Post-Vaccination 1 (Day 07 Post-Vaccination 2) Visit Procedures for Cohorts 2 and 4

- 1) Review medical history, including past and ongoing medication since the last visit.
- 2) Perform a focused clinical examination including temperature, pulse, and respirations, EENT, respiratory, cardiac and lymphatic system.

- 3) Obtain a nasal swab sample for quantification of vaccine virus shedding. If the participant meets criteria for an Illness Visit, the same nasal swab specimens may also be tested for respiratory pathogens.
- 4) Review the solicited reactions and unsolicited AEs, AESIs, MAAEs and SAEs in the completed DC3 / eDC with the participant's parent / guardian / legally authorized representative.
- 5) If an SAE occurred, follow the instructions in [Section 10](#) for reporting it. Remind to notify the site in case of an SAE.

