- 6) Complete the relevant CRFs for this visit.

Visit 05: D84+8 Post-Vaccination 1 (Day 28+8 Post-Vaccination 2) Visit Procedures for Cohorts 2 and 4

- 1) Review medical history, including past and ongoing medication and immunizations since the last visit.
- 2) Perform a focused clinical examination including temperature, pulse, and respirations, EENT, respiratory, cardiac and lymphatic system.
- 3) Obtain a blood sample for serum antibodies to RSV.
- 4) Collect and review the solicited reactions and unsolicited AEs, AESIs, MAAEs and SAEs in the completed DC3 / eDC with the participant's parent / guardian / legally authorized representative. Provide MA.
- 5) If an SAE had occurred, follow the instructions in [Section 10](#) for reporting it. Remind to notify the site in case of an SAE.
- 6) Complete the relevant CRFs for this visit.

Visit 99: Illness Visits

Illness visits can be conducted remotely, as a home visit or an onsite visit depending on the judgment of the investigator. The requirement for an Illness Visit and which type of illness visit will be evaluated first by video call. The video call will be used to initially remotely evaluate the study participant's clinical status and whether the illness can be managed remotely especially for mild (Grade 1) illness. This staged management of illness visits is required during the current COVID-19 pandemic situation to limit the number of contacts between the study participant and study site staff to only those that are absolutely required. Guidelines for remote evaluation are described in the Operating Guidelines.

The timeframe after site notification in which the Illness Visit must occur, if deemed necessary by the Investigator, depends on grading of the fever and respiratory symptoms and the phase of the study. If the Illness Visit occurs on a day concurrent with a routine Study Visit when a nasal swab specimen is to be collected, the same nasal swab specimen would be used to test for respiratory pathogens. A second nasal swab should be collected 48 hours later. If the Illness Visits occurs on a day concurrent with a routine Study Visit when a nasal swab specimen is not collected, a nasal

swab specimen is required to test for respiratory pathogens. A second nasal swab should be collected 48 hours.

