If illnesses/safety events occur, the study participant should be managed according to the site/local standard of care, including the conduct of lab investigations required for diagnosis and/or management of the study participant. Following an Illness Visit, medical personnel should continue to follow participants until resolution.

Illness visits may occur at any time during the study. The Illness visit timeframes are summarized in [Table 5-4](#).

Table 5-4: Illness visit timeframe

Phase	Symptom	Grade	Visit timeframe
Acute (post-vaccination to midnight 28 days after each vaccination)*	Fever, acute otitis media or URI	1	Within 3 days
		> 1	Within 2 days
	LRI	Any	Within 2 days
	SAEs	Any	Within 2 days
Post-acute (12:01am on 29 th day after post-vaccination to midnight 56 days after each vaccination)*	SAEs	Any	Within 2 days
RSV surveillance season (on average, 01 November to 31 March for NH and 01 May to 30 September for SH)*	Medically attended fever, acute otitis media, URI or LRI	>2	Within 3 days
	SAEs	Any	Within 2 days
Post-RSV season (on average, 01 to 31 April for NH and 01 to 31 October for SH) or at least 5 months after last vaccine administration	SAEs	Any	Within 2 days

LRI, lower respiratory tract illness; NH, Northern hemisphere; RSV, Respiratory Syncytial Virus; SAE, serious adverse event; SH, Southern hemisphere; URI, upper respiratory tract illness

*In some circumstances, acute phase or post-acute phase may overlap with the RSV surveillance season, in which case the more conservative visit timeframe should be considered.

Illness Visit procedures are as follows:

- 1) Obtain verbal medical history about the participant, including past and ongoing medication and immunizations.
- 2) Determine whether the participant can be managed remotely or if an at home visit or an onsite illness visit is required.
- 3) If an at home or onsite visit, perform a focused clinical examination including temperature, pulse, and respirations, EENT, respiratory, cardiac and lymphatic system. Instructions for

conducting a focused clinical examination remotely are described in the Operating Guidelines.

- 4) Collect and review the solicited and unsolicited AEs, AESIs, MAAEs and SAEs in the completed DC / eDC or memory aid with the participant's parent / guardian / legally authorized representative.

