- 5) If an SAE had occurred, follow the instructions in **Section 10** for reporting it. Remember to notify the site in case of an SAE, if illness starts within the 28 days of vaccination.
- 6) Obtain a nasal swab sample for RSV viral detection and [REDACTED] for respiratory pathogens.
- 7) COVID-19 testing if required according to the opinion of the investigator and CDC COVID testing algorithm.^a
- 8) Complete the relevant CRFs for this visit.
- 9) Schedule follow-up as appropriate, including a visit for the collection of a confirmation nasal swab 48 hour later.
- 10) If illnesses/safety events occur, the participant should be managed according to the site/local standard of care, including the conduct of lab investigations required for diagnosis and/or management of the study participant.

Specific guidance for illness visits, including use of personal protective equipment (PPE) for full contact and droplet precaution, are described in the Operating Guidelines.

Follow-up of participants with solicited reactions or with AEs That Led to Study/Vaccination Discontinuation:

Unless a participant or participant's parent / guardian / legally authorized representative refuses further contact, each participant who experiences an AE (whether serious or non-serious) during the study must be followed until the condition resolves, becomes stable, or becomes chronic (even after the end of the participant's participation in the study) if either of the following is true:

1. The AE is considered by the Investigator to be related to the product administered.
2. The AE caused the discontinuation of the participant from the study or from vaccination.

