During the RSV season (01 November to 31 March in the northern hemisphere and 01 May to 30 September in the southern hemisphere) or post-vaccination RSV surveillance (at least 5 months after last vaccine administration), make phone contacts every 2 weeks with the parent / guardian / legally authorized representative.

- 1) Record relevant information concerning the participant's health status including any changes in medications and immunizations on the telephone contact form.
- 2) Schedule an Illness Visit within the guidelines and stipulated time frame from the phone contact for a medically attended illness of the following types: fever, URI, LRI or otitis media. If this illness overlaps with the Acute or Post-Acute Phases, the time frames specified for the relevant Acute or Post-Acute phase should be used (see [Table 5-4](#)).

- 3) If a participant had visited any other non-study doctor / hospital for a serious adverse event (SAE) (at any time in the study), schedule a site visit once the participant is discharged to obtain a nasal swab sample for RSV viral detection and [REDACTED] for respiratory pathogens.
- 4) If an SAE had occurred, follow the instructions in [Section 10](#) for reporting it. Remind to notify the site in case of an SAE.

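### Instructions to parents for RSV surveillance name only SAEs in some places and any illness in others; under the SAE-only text a first swab can come up to 17 days after onset

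*Protocol*

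**What the plan says.** **SAE-only text.** Protocol 5.1.1 says that the parent "receives a memory aid (MA) to record the SAEs from the D56 visit until the end of the study" in Cohorts 1 and 3, and from the D84 visit in Cohorts 2 and 4. In 5.1.4.1, the visits at which the memory aid is handed over (Visit 03 in Cohorts 1 and 3, Visit 05 in Cohorts 2 and 4) carry the step "Remind to notify the site in case of an SAE". The surveillance calls in 5.1.4.2 carry the same step. At the last visit the instruction is "Review the MA for SAEs with the participant's parent / guardian / legally authorized representative". Section 9.1.1.1 limits the Post-Acute Phase instruction to symptoms that suggest an SAE.

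**Wider text.** Visit 01 (all cohorts) and Visit 03 (Cohorts 2 and 4) remind parents to report an SAE or any illness, with no end date. The diary-card bullet in 5.1.1 asks them to alert the site to symptoms of respiratory tract illness. The Illness Visit steps review AEs, AESIs and MAAEs, as well as SAEs, in the diary card or memory aid. Section 11.1 describes a questionnaire for SAEs, MAAEs and AESIs and a memory aid for events in general.

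**Timing.** In surveillance, sites are to "make phone contacts every 2 weeks with the parent / guardian / legally authorized representative" and then "Schedule an Illness Visit within the guidelines and stipulated time frame from the phone contact for a medically attended illness". Table 5-4 allows 3 days for "Medically attended fever, acute otitis media, URI or LRI", but its surveillance row is limited to Grade >2. The clock is described as "The timeframe after site notification in which the Illness Visit must occur, if deemed necessary by the Investigator".

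**The concern.** RSV MAARI and MAALRI require an RSV-positive respiratory sample (Protocol 9.3.4.1, SAP 4.4.3). A true RSV illness that is swabbed too late counts as a non-case. The clock runs from notification or the call, never from onset, so the reporting instruction decides how late a swab can be. A parent who follows the most recent reminder would not phone about a non-serious illness between calls.

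Two results are exposed. The first is the exploratory case counts, and the vaccine efficacy that SAP 5.1.3 computes from them. The second is the post-season titers, a secondary endpoint. Data are excluded after wild-type RSV only from the date of a laboratory-confirmed infection (Protocol 12.2.1, SAP 5.1.1.2), so an infection missed by swab stays in. The SAP derives no interval from onset to swab, so the report could not show how often this happened.

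**Working it through.** The documents state no onset-to-swab delay, so there is no figure of theirs to reproduce. The delay follows from their timing rules.

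**Inputs**
- Call interval: 14 days (Protocol 5.1.4.2).
- Illness Visit window in surveillance: 3 days after notification (Table 5-4, Grade >2 row).
- Second swab: 48 hours after the first (5.1.4.1, "including a visit for the collection of a confirmation nasal swab 48 hour later").
- Assumptions: the illness is not reported before the next call, and onset is uniform between two calls.

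**Check on the interval.** The season is 151 days in the north (1 November to 31 March) and 153 in the south (1 May to 30 September). 151/14 = 10.8 and 153/14 = 10.9 calls. The procedures table for Cohorts 2 and 4 plans contacts 31 to 40 (42), that is 10 to 12 calls, which agrees.

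**Maximum.** First swab: 14 + 3 = 17 days after onset. Second swab: 17 + 2 = 19 days.

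**Distribution under the assumptions.** Delay D = U + V, with U uniform on 0 to 14 days and V the days from call to visit. Mean = 7 + E(V). For k of 7 or 10, P(D > k) = (14 − k + E(V))/14. For k = 14, P(D > 14) = E(V)/14.

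| Visit after call | Mean | P(>7 days) | P(>10 days) | P(>14 days) |
|---|---|---|---|---|
| Same day, E(V) = 0 | 7.0 | 7/14 = 50% | 4/14 = 29% | 0% |
| Uniform 0–3 days, E(V) = 1.5 | 8.5 | 8.5/14 = 61% | 5.5/14 = 39% | 1.5/14 = 11% |
| Day 3, E(V) = 3 | 10.0 | 10/14 = 71% | 7/14 = 50% | 3/14 = 21% |

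**If the parent notifies at onset instead,** the wait for a call disappears: first swab within 3 days, second within about 5.

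**Does the earlier any-illness reminder carry over?** In Cohort 3, Visit 01 was planned for 1 April to 31 May 2021 (5.1.5) and the season opens on 1 November, 154 to 214 days later. In between, Visit 03 gives the SAE-only reminder and hands out the memory aid. In Cohorts 2 and 4 the any-illness reminder at Visit 03 is followed about 28 days later by the SAE-only one at Visit 05.

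**The case against.** The strongest reply is that surveillance is not SAE-only, and a reader who inferred that from the reminders alone would go too far. The any-illness reminders have no end date; all 300 planned participants get one at Visit 01, and the 220 in Cohorts 2 and 4 get a second at Visit 03. Each 2-weekly call records health status and schedules an Illness Visit for a medically attended fever, URI, LRI or otitis media. Hospitalized RSV is an SAE, to be notified at once with a visit within 2 days, so the 14-day wait does not reach the most severe cases. Where surveillance overlaps the Acute Phase, the diary and frequent calls also apply (5.1.2). All of this stands. It makes the problem a conflict between passages and makes 17 days a worst case, but it does not tell a site which instruction governs.

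It also stands that the post-season sample is drawn to find infections that surveillance missed, and that the SAP repeats the immunogenicity analysis without the wild-type exclusion. Neither closes the gap. Serology cannot supply the positive swab that a MAARI case needs, and an unconfirmed infection is present in both versions of the immunogenicity analysis.

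A reader might further infer that late swabs would create apparent efficacy, on the reasoning that vaccinees shed for less time. The documents do not support this. They give no wild-type shedding duration, no detection rate by day and no swab sensitivity by arm, and follow-up is the same in the blinded arms. If sensitivity is equal in the arms, 1 minus the risk ratio is unbiased and only precision is lost.

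**Conclusion.** The point holds as an inconsistency with a bounded consequence. The reminder and memory-aid passages contradict each other and must be reconciled. Under the SAE-only text, a non-serious medically attended respiratory illness outside the Acute Phase can wait until the next call, and its first swab can come up to 17 days after onset. The means of 7 to 10 days apply only if no parent calls between contacts and onset is uniform. The 3-day window is stated only for Grade >2; Table 5-4 gives no surveillance window for lower grades, so 17 days is not a stated limit for them.

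The number of cases lost, and any difference between arms, cannot be derived from the documents. The endpoints most affected are exploratory, all analyses are descriptive, and dose selection rests on safety, infectivity and immunogenicity (5.1.2). This is a cheap improvement to make, not a threat to the trial's main conclusions.

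**What to change.** - At Visit 03 (Cohorts 1 and 3), Visit 05 and the 2-weekly surveillance calls, change the reminder to: an SAE or any medically attended fever, otitis media, URI or LRI.
- Add these illnesses to the memory aid and to its review at Visit 04 (Cohorts 1 and 3) or Visit 06 (Cohorts 2 and 4), and bring 5.1.1 into line with the Illness Visit steps and section 11.1.
- Optionally, derive days from illness onset to swab in SAP 4.4.3 and report them descriptively by vaccine group. A vaccine-efficacy analysis restricted to swabs within 7 days is not advised: that cut-off has no basis in the documents, it would discard some of the few cases, and it cannot recover late false negatives.

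The cost is wording in the visit and call lists and the memory aid, plus one optional derived variable. Some parent calls and illness visits would happen earlier, with few added. For visits already completed only the descriptive delay remains available, and only if onset and swab dates were recorded.

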5.1.2 Justification of the Study Design

For this Sanofi Phase I/II trial, data will be analyzed according to serostatus. Baseline serostatus will be retrospectively determined from serum samples collected at baseline. Participants will be categorized into RSV-experienced or RSV-naïve based on the presence or absence of detectable serum RSV anti-F IgA antibodies. This biomarker has been chosen since it is produced only in response to RSV infection and not transferred trans-placentally from mother to child.

Evaluation of post-vaccination immunogenicity on Day 56 for Cohorts 1, 2, 3 and 4 and Day 84 for Cohorts 2 and 4:

To date, all studies with live-attenuated RSV candidate vaccines have used Day 56 as the time point to assess serum antibody response post-vaccination with a single dose administration. This time point is used for two reasons: 1) since this is a primary response (rather than an anamnestic [memory] response), serum antibody response may not have reached maximal levels by Day 28 and 2) maximal replication of these highly attenuated vaccine viruses does not typically occur until Day 7, which may also delay induction of the immune response. In participants receiving 2 administrations of vaccine, this is no longer likely to be a primary response and rather an anamnestic (memory) response and serum antibody response is likely to be maximal by Day 28 after the second vaccination.

RSV season or post-vaccination RSV surveillance for Cohort 4:

Based on previous data regarding the seasonality of RSV in the US, Canada, Chile, Honduras, and South Africa, surveillance for RSV-associated disease will be largely conducted during the NH (1st November to 31st March) and SH (1st May to 30 September) RSV seasons respectively, adjusted for local site RSV seasonality. Due to the disruption of the seasonal pattern of RSV globally (24) (25), it is unclear when the normal seasonal transmission will resume though there is some suggestion of a rebound in the winter of 2021–2022 in the NH (26). Because of the unpredictability of the RSV season due to the impact of COVID-19 nonpharmaceutical interventions, study participant enrollment and vaccination will continue regardless of RSV activity. Study participants enrolled before the routine winter RSV season for that locality will be followed up until the consequent month after the end of the routine season (i.e. April for NH and October for SH). Study participants enrolled during the routine RSV season (i.e. November to March for NH and May to September for SH) will be followed up for at least 5 months after the last vaccine administration. During the RSV season or post-vaccination RSV surveillance, study participants will be monitored for symptomatic medically attended respiratory illness. Note, this surveillance may overlap with the Acute and Post-Acute phases. In this case, evaluations required for each of the relevant phases of the study will be conducted.

Evaluation of two vaccine doses [REDACTED]:

Previous Phase Ia studies done by the NIH have demonstrated that the [REDACTED] dose of RSV ΔNS2/Δ1313/I1314L vaccine resulted in better infectivity and neutralizing antibody seroresponse than the [REDACTED] dose, with no evidence of an excess of respiratory tract illness associated with receipt of the higher dose ([REDACTED]). However, in these studies, the vaccine was administered intranasally using a sterile, needle-less 1 mL oral syringe, at a volume of 0.5 mL as nasal drops (approximately 0.25 mL per nostril). In VAD00001 study, the vaccine would be administered at a total volume of [REDACTED] [REDACTED] [REDACTED]

Use of an intranasal [REDACTED]
may improve the overall delivery of the vaccine and may increase replication in both doses. Use
of the [REDACTED] may also improve the infectivity of the low dose [REDACTED]
doses will be the minimal doses explored using the [REDACTED]

Evaluation of two administrations of vaccine doses:

There are several published studies evaluating 2 or 3 administrations of attenuated RSV or parainfluenza virus type 3 (PIV3) candidate vaccines (5) (6) (9) (27) (28) (29) (30) (31) (32). Generally, there was a high level of restriction of the second administration, and limited serum immune responses. The main effect was vaccine infectivity in the individuals who did not respond to the first administration. Two administrations of RSV Δ NS2/ Δ 1313/I1314L may improve the infectivity of either dose.

Selection of vaccine dose using safety, infectivity, viral shedding and immunogenicity in infants and toddlers regardless of baseline RSV serostatus:

Given the plan for a future liquid formulation in which the targeted dose will decay over the shelf life of the product, the dose selection based on this study relates to the future clinical development with frozen product. The data will be analyzed for comparable safety, infectivity, and immunogenicity profile between the two doses utilized in this study to justify clinically the future dose range boundaries of the non-frozen liquid formulation for final commercialization. The vaccine dose for the frozen liquid product to be utilized in future late-stage studies is expected to be around mid-range of the planned operative range for the future liquid formulation of [REDACTED].

Therefore, an unblinded interim analysis for dose confirmation of RSV Δ NS2/ Δ 1313/I1314L vaccine is planned on participants from Cohorts 1, 2 and 3 and at least 90 participants enrolled in Cohort 4. The interim analysis will take place when participants have provided safety data up to the D84 timepoint and have D84 immunogenicity results available. Based on the results of this analysis, the dose for future clinical studies (frozen product) will be confirmed. The acceptability of safety, infectivity, and immunogenicity results of the two doses tested to justify clinically the future dose range boundaries of the non-frozen liquid formulation for final commercialization will also be descriptively assessed. The selected dose will then be confirmed during an early analysis.

An unblinded early analysis is planned on all participants when they have provided safety data up to the D84 timepoint and have D84 immunogenicity results available. Based on the results of this analysis, the dose for future studies will be confirmed.

Placebo group:

Placebo recipients will be included in each cohort to establish the background rates of respiratory and febrile illnesses that occur in infants and toddlers.

Clinical hypothesis:

Both doses of the live-attenuated RSV Δ NS2/ Δ 1313/I1314L vaccine are anticipated to be safe and immunogenic in infants and toddlers. However, administration of either dose may be associated

with adverse events that become apparent only when analyzed in a larger number of participants than the numbers enrolled in Laboratory of Infectious Disease (LID)/ National Institute of Allergy and Infectious Diseases (NIAID)/NIH Phase Ia studies, where each study assessed 10 to 40 vaccinees. Additionally, the rate, magnitude and durability of antibody responses may differ according to dose, as well as the magnitude of the memory (anamnestic) seroresponse observed following naturally occurring RSV infection. The intranasal [REDACTED] device used in this study may also impact the safety and immunogenicity of the vaccine. Dose selection will be based on a descriptive comparison of the safety, infectivity and immunogenicity of 1 or 2 administrations of either dose category.

